The intervention will consist of randomizing subjects to one of three arms. Subjects will either be assigned to OCP + Placebo, Metformin + Placebo or OCP + Metformin. Metformin will be initiated in a step-up fashion using extended release pills as they are associated with fewer gastrointestinal side effects. Subjects will begin with one tablet of metformin every night for 5 days, eventually building up to 4 tablets every night, with the maximum dose of metformin being 2000 mg. In regards to OCP, previous randomized clinical trials (RCTs) have shown that 20mcg ethinyl estradiol/norethindrone 1.0 mg was well tolerated. The study will utilize a 20mcg OCP but a less androgenic third generation progestin (desogestrel 0.15mg) with potentially lesser impact on lipids and insulin sensitivity. All subjects with no menses the 3 months prior to screening will be given medroxyprogesterone acetate, at the screening visit, after a negative pregnancy test (in order to induce menses). Placebo pills will be administered to individuals randomized to OCP or metformin only in order to maintain study blinding. Subjects will undergo 6 in person study visits and life style modification counseling regarding diet and exercise. Patient contact will be made via the subject's preferred contact method after randomization and at the end of each month when there is no in person visit to ensure study compliance with medications, keeping study logs and to review side effects.

Primary efficacy parameter

Determine the prevalence of MetS after randomizing to OCP, metformin or OCP+metformin for 6 months. MetS will be defined by NCEP ATPIII criteria as the presence of at least 3 of the following 5 criteria: TG≥150mg/dl, HDL-C<50mg/dl, BP≥130/≥85mmHg, WC>88cm and fasting glucose≥100mg/dl.

Secondary/Tertiary efficacy parameters

Assess change in HDL-C function, serum apolipoproteins, lipid particle size and number, body fat distribution, BMI, serum adipokines, HbA1c, glucose and insulin sensitivity, serum markers of inflammation, free fatty acids, androgens, quality of life parameters, cognitive testing and predictive factors for change in prevalence on MetS.

Subjects will have the option to consent to storage of their blood for future additional analysis as related to the disease of interest. No research/future analysis will take place, prior to gaining IRB approval.

Statistical Analysis

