The primary analysis will use an intent-to-treat paradigm, wherein all randomized subjects are included according to their randomized treatment arm. Data will be summarized using descriptive statistics for continuous variables and frequency statistics for categorical variables. For the primary outcome of the presence of MetS at the end of the trial, logistic regression will be used with independent variables that include terms for the treatment arm and the 3 randomization stratification factors as covariates, with a contrast constructed to test for linear trend over the three treatment arms. For secondary continuous outcomes, linear mixed-effect models will be fit to assess differences between the treatment arms with respect to changes in these outcomes over time. The independent variables in the model will be treatment arm, time, the interaction of treatment and time and the 3 randomization factors as covariates.

Anticipated time to completion

A total of 5 years (2017-2022) is anticipated. 3.5-year enrollment period (based on 3 subjects per site/month x 2 sites), 6-month treatment period followed by time for analyses and interpretation of the data.

Regulatory Compliance

A data safety and monitoring board, led by [name], has been established to ensure that patient safety and clinical study data and regulatory requirements are met regarding the Food and Drug Administration (FDA) code for federal regulations. This trial is registered on http://www.clinicaltrials.gov

Study Objectives

Primary Aim

Our primary goal is to determine the effect of 6 months' treatment with OCP vs. metformin vs. OCP + metformin on prevalence of MetS and its components in overweight / obese women. Implicit in the primary aim is clearly defining MetS, by NCEP ATPIII criteria as the presence of at least 3 of the following 5 criteria: TG≥150mg/dl, HDL-C<50mg/dl, BP≥130/≥85mmHg, WC>88cm and fasting glucose≥100mg/dl; and the goal of tracking safety of our interventions throughout the study (through safety lab evaluations, vital signs and diaries).

Secondary Aim

The study will assess secondary outcomes such as defining the effects of OCP (lowering androgens) verses metformin (improving insulin sensitivity) verses OCP + metformin on body fat distribution, glucose tolerance, adipokines and markers of inflammation.

- 1. Assess change in HDL-C function by measuring reverse cholesterol efflux capacity.

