- 2. Subjects will be diagnosed with PCOS defined by the most up to date Rotterdam criteria based on:
 - a. Androgen excess

And

b. polycystic ovaries.

Or

- c. A history of chronic anovulation or spontaneous periods.
- 3. BMI \ge 25 kg/m² to \le 48 kg/m² obtained at screening visit.
- 4. In good general health according to the investigators discretion
- 5. Willing to avoid pregnancy for the duration of the study.

Exclusion Criteria

- 1. Current pregnancy or desire of pregnancy during course of study
- 2. Currently breastfeeding
- 3. Known 21 hydroxylase deficiency or any form of congential adrenal hyperplasia (CAH)
- 4. Untreated thyroid disease (TSH \leq 0.45 mlU/mL and \geq 4.5 mlU/mL)
- 5. Untreated hyperprolactinemia (2 Levels≥30 ng/ml at least one week apart)
- 6. Type 1 or type 2 Diabetes Mellitus currently receiving anti-diabetic agents, (subjects may wash out from metformin if taking the drug for another indication.)
- 7. Liver disease (AST/ALT \geq 2 times normal or a total bilirubin \geq 2.5 mg/dL)
- 8. Renal disease (BUN≥30 mg/dL or serum creatinine ≥1.4 mg/dL)
- 9. Anemia (hemoglobin ≤10 mg/dL)
- 10. current history of alcohol abuse (≥ 22 drinks/week in the past 3 months)
- 11. Poorly controlled hypertension defined as average systolic blood pressure >= 150 mm Hg or average diastolic ≥100 mm Hg obtained on three measurements obtained 5 minutes apart. If treated, average systolic blood pressure ≥140 mm Hg or average diastolic ≥90 mm Hg
- 12. Patients with a history of, or suspected cervical carcinoma, endometrial carcinoma
- 13. TG≥250mg/dl
- 14. Current Use of lipid lowering or weight loss agents
- 15. Current use of hormonal contraceptives such as oral contraceptives, depo progestin, or hormonal implants
- 16. Participation in any study of an investigational drug or device or biological agent within 30 days
- 17. Suspected adrenal or ovarian tumor secreting androgens
- 18. Suspected Cushing's syndrome
- 19. Bariatric surgery procedure in the recent past (≤12 months)
- 20. Absolute contraindications to the use of hormonal contraceptives or metformin (details in MOP)
- 22. subjects who are unable to comply with the study procedures, (In the opinion of the investigator,)

***Note:** the study will allow rescreening of subjects. When subjects are re-screened a new consent form will be signed and a new study number will be assigned.

Study Termination Criteria

- 1. Development of diabetes as defined in the manual of procedures

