No other interventions, other than those specified in the protocol are allowed to treat PCOS or weight management during participation in the study.

Adherence Assessment

Adherence to the interventions will be monitored by the use of medication reconciliation, diary compliance and by monthly visits on site or contact with the subject.

Clinical and Laboratory Evaluations

Schedule of Evaluations

The table below summarizes the clinical and laboratory evaluations during the trial. A description of the visits follows. Note, prior to the screening visit, subjects may prescreen for potential eligibility.

Study Visit Schedule	Screening (half of the visit as a remote option)	Randomization	Randomization Patient Contact (PC)	4 Week Visit (remote option)	8 Week Visit (remote option)	12 Week PC	16 Week Visit	20 Week PC	24 Week Visit	Early Termination Visit (> or equal to 12 weeks of medication)	End of study PC
Sign Informed Consent	x										
Medical History Questionnaire	x										
Screening labs	x*										
DNA Sample		х									
Safety Labs	x*	х					x		x	x	
Menstrual History	x	х		x	x		x		x	x	
Urine Pregnancy Test	x	х		x	x		x		x	x	
Vitals and Biometrics	x	х		x	x		x		х	x	
Hirsutism Assessment	x	х							x	x	
Transvaginal Ultrasound	x*	х							x	x	
Fasting labs		х					x		x	x	
OGTT labs		х							x	x	
DXA Scan		х							x	x	
Lifestyle Modification		х					х				
ASA 24						x			х	x	
Acne Assessment		х							х	x	
HRQOL – PCOS, STAI, CES-D, FSDS-R, FSFI &		х							x	x	

Table 6: Study Visits and Procedures

Cognitive testing Questionnaires											
Randomization		х									
Dispense Medication/Log		x		x	x		х				
Collect Medication/Log				x	x		x		х	х	
Review Concomitant Medications	x	х	х	x	x	x	x	x	x	x	x
Review Adverse Events			x	x	x	х	х	х	х	х	x

*As Needed

Timing of Evaluations

7.2.1 Screening visit:

- 1. Obtain informed, signed consent from subject.
 - Subject must specifically be made aware of potential drug side effects and adverse outcomes.
 * Remote option for e-consent via REDCap, utilization of this option at PI discretion
- 2. Complete medical assessment.
 - At the Screening Visit, a detailed general medical history for the former 6 months (longer in case of gynecological relevance) and history of concomitant diseases or interventions is to be reviewed and to be documented.
 - * Remote option for completion, utilization of this option at PI discretion
- 3. Must obtain and record menstrual history.

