7.2.10 Week 25 patient contact

This contact will be made one week after patient has completed taking the medication to review any side effects and answer any patient questions. This patient contact will close out the study adverse events.

Study Risk and Benefits

Risk

The risks of these studies include the risks of the study procedures, and the risk of the study interventions. These will be discussed separately below.

Risks of Study Procedures

These risks include the risk of phlebotomy, oral glucose tolerance test and DXA. The risks of phlebotomy include pain at the phlebotomy site, bruising and rarely bleeding, and potentially iatrogenic anemia. Risks of the oral glucose tolerance test include the risks of multiple phlebotomy or in some cases the risk of insertion of an IV. The risks of IV insertion include the risks of phlebotomy, and additionally the induction of anemia, and infection at the site. Glucose ingestion can cause nausea and in rare instances vomiting upon ingestion. We have never experienced an allergic reaction to the oral glucose solution, though this is possible. Some subjects also may experience an episode of hypoglycemia after the test which can present with increased heart rate and anxiety. In the most severe cases, fainting can occur. The DXA scan will involve exposure to radiation, on average 2-3 milliroentgens of radiation during the procedure. The average amount of radiation that a person would receive from a DXA scan is less than 1% of the background radiation experienced from living in the Philadelphia area for one year, for example.

Risks of Study Interventions

Oral Contraceptive Pill - OCP used in this study is low dose (20micrograms ethinyl estradiol), which may cause bloating, nausea, breast tenderness, mood changes, weight change and headaches. Common side effects include breakthrough bleeding and amenorrhea. OCP are also associated with increased risk for cardiovascular disease, especially venous thromboembolism and stroke. OCP can also cause hypertension and alter blood lipid and glucose levels. Interactions with drugs such as phenobarbital, phenytoin, and rifampin increase the metabolism of oral contraceptives, thus decreasing the effectiveness as a method of birth control. Table lists all side effects recorded in women in the OCP arm of the recently completed OWL-PCOS study (n=49). Roughly same numbers are expected in this current study.

OWL-PCOS study	Number of		Number of

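### The MetS blood pressure component counts the reading alone, so a woman whose hypertension is controlled by a drug can be scored free of it at baseline and at month 6

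*Combined protocol and SAP*

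**What the plan says.** The Synopsis (Primary efficacy parameter) and the Primary Aim define MetS as "the presence of at least 3 of the following 5 criteria": "TG≥150mg/dl, HDL-C<50mg/dl, BP≥130/≥85mmHg, WC>88cm and fasting glucose≥100mg/dl". No component has a clause for drug treatment.

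Exclusion item 11 removes women with poorly controlled hypertension and gives a stricter limit for those already on treatment: "If treated, average systolic blood pressure ≥140 mm Hg or average diastolic ≥90 mm Hg". Treated women under that limit are therefore admitted. Two other kinds of drug that act on MetS components are handled at entry by exclusion: "Current Use of lipid lowering or weight loss agents" (item 14) and "Type 1 or type 2 Diabetes Mellitus currently receiving anti-diabetic agents" (item 6).

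The Concomitant Interventions section restricts only other treatment of PCOS or weight. Table 6 has a row, "Review Concomitant Medications", marked at every visit and contact. The Outcomes and Statistical Analysis sections do not say how that information enters the MetS outcome.

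Baseline MetS is also a randomization stratum and a covariate in every model. Under Risks of Study Interventions the protocol states: "OCP can also cause hypertension and alter blood lipid and glucose levels". Two rules take women out of the study: development of hypertension as the manual of procedures defines it (Study Termination Criteria, item 2), and a pressure above 150/100 mmHg on two occasions (section 8.2.1).

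**The concern.** A woman with known hypertension whose drug holds her at, say, 125/80 is recorded as not having the blood pressure component. The reading then reflects the drug and not her metabolic state. One definition feeds the month-6 outcome, the baseline stratum and the covariate, so the error can enter all three.

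Blood pressure is not a marginal component here. The study hypothesis names a rise in blood pressure as one way OCPs increase MetS. Table 2 of the Background shows the component in 31.9% of White and 45.5% of Black women with PCOS, against 4.9% and 18.8% for glucose. Under a three-of-five rule it will sometimes decide MetS status.

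Two things are at stake. Reported prevalence may be too low. And if an antihypertensive is started or increased because an OCP raised blood pressure, part of the effect under study could drop out of the endpoint in the two arms that take an OCP.

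**Working it through.** **When a treated woman is misclassified.** Taking either limit, 130 systolic or 85 diastolic, as sufficient:

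- Treated, at 130-139 systolic or 85-89 diastolic: eligible, and the component still counts. No error.
- Treated, below 130/85, with none, one, or three or more other components: the component is lost but MetS status is the same either way.
- Treated, below 130/85, with exactly two other components: scored as no MetS, although blood pressure would have been her third component. This is the only case that changes the primary outcome.

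**How many.** The documents give no rate of antihypertensive use. As an assumption only: 5-10% treated, 40-60% of these below 130/85, and 30-50% of those with exactly two other components. Then 0.05 × 0.4 × 0.3 = 0.6% and 0.10 × 0.6 × 0.5 = 3.0% of women change status, or 0.5 to 2.4 per arm of 80.

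**The plan's power.** Inputs from Sample Size and Power Calculations: 26%, 40% and 50% in the metformin, OCP+metformin and OCP arms; 240 randomized, 204 evaluable, so n = 68 per arm; two-sided 5% trend test. With equally spaced scores and a continuity correction:

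- T = n(p3 − p1) − 0.5 = 68 × 0.24 − 0.5 = 15.82
- V0 = 2n·p̄(1 − p̄) = 2 × 68 × 0.3867 × 0.6133 = 32.25, root 5.679
- V1 = n[p1(1 − p1) + p3(1 − p3)] = 68 × (0.1924 + 0.2500) = 30.08, root 5.485
- Power = Φ[(15.82 − 1.96 × 5.679) / 5.485] = Φ(0.855) = 80.4%

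This reproduces the stated 80%. The same method gives 84.0, 89.2, 80.4, 86.4 and 79.7% for the five rows of Table 10, against 84, 89, 80, 86 and 80%.

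**Loss spread over all arms.** Treatment at entry should be balanced by randomization. Take 26/40/50 as the rates with treated women counted, and remove cases from every arm:

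| Loss in every arm | Rates scored (%) | Power |
|---|---|---|
| none | 26 / 40 / 50 | 80.4% |
| 1 point | 25 / 39 / 49 | 80.8% |
| 2 points | 24 / 38 / 48 | 81.2% |
| 2% of cases | 25.5 / 39.2 / 49.0 | 79.0% |
| 5% of cases | 24.7 / 38.0 / 47.5 | 76.8% |
| 10% of cases | 23.4 / 36.0 / 45.0 | 73.0% |

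An equal loss in points keeps the 24-point difference and slightly lowers the variance. A proportional loss shrinks the difference, because more cases go from the arm that has more. Which pattern applies depends on how many women in each arm have exactly two other components, and the documents do not say.

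**Drugs started or increased on study.** A woman above 130/85 but short of both termination rules may, on the protocol text, be treated and stay. A woman who leaves after at least 12 weeks of medication has an early termination visit with vital signs and fasting labs (section 7.2.9), and treatment could begin before it. The manual's definition of hypertension sets how many women this covers. It is not in the documents, so no figure is calculated.

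**The case against.** The case for leaving the definition alone has four parts.

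- **Termination.** Women whose blood pressure rises enough on an OCP are to leave the study, not to be treated and scored negative at month 6. This stands for those who meet the rules. It does not reach women treated below those limits, or treated before an early termination visit whose reading is used.
- **Randomization.** Use of antihypertensives at entry should not differ between arms, so a reader who infers a general bias towards no difference goes too far. This stands. The entry route can leave power unchanged.
- **Blood pressure is not unique.** Items 6 and 14 concern current use at entry. The protocol text no more bars starting a lipid-lowering drug on study than it bars an antihypertensive. This stands: the contrast between blood pressure and the other components holds at entry only.
- **Unseen manual.** Wash-out drugs and contraindications are detailed in the manual of procedures, which may restrict antihypertensives. This stands as a limit on the claim, which is about the protocol text.

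A reader might also infer that every treated woman loses the component, or take the loss from the OCP arm alone and quote a lower power. The documents support neither. Treated women at 130-139 or 85-89 still count. Nothing in the documents estimates OCP-prompted treatment, and the OCP+metformin arm takes the same OCP.

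**Conclusion.** The gap is real and modest. The endpoint ignores drug treatment of a component that eligibility allows to be treated, and no analysis rule fills the gap.

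For treatment at entry the consequence is mainly understated prevalence, with some women placed in the wrong baseline stratum. Power stays at about 79-81% against 80.4% for a loss of 1-2 points in every arm or 2% of cases. It would fall to 76.8% or 73.0% only if 5% or 10% of cases were lost in proportion to each arm's rate, and the documents give no basis for choosing among these. All of this rests on an assumed frequency of treatment.

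For drugs started or increased on study, an OCP effect could be partly hidden in both OCP arms. The termination rules narrow this, and what remains cannot be sized without the manual's definition. No power figure confined to the OCP arms should be claimed.

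The change is still worth making: it concerns the primary endpoint, it is cheap, and without it the handling could be settled after the data are seen.

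**What to change.** In the MetS definition, state that the blood pressure component is present when the reading is at or above 130/85 mmHg or the woman is taking a drug for hypertension at that visit. Apply this at baseline and at month 6, or at the early termination visit if its data are used for the outcome. Take drug use from the concomitant medication record, and confirm that the record captures the indication.

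Keep the baseline MetS stratum as randomized for the covariate. Report the measured-only definition as a sensitivity analysis, with the number of women on antihypertensives by arm at both time points.

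The cost is one sentence in the definition and one extra analysis. The sample size and clinical care do not change. The downside is slightly weaker comparability with the earlier OCP trial, if that trial used measured values only.

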- 2. Development of hypertension as defined in the manual of procedures
- 3. Unable to tolerate study medications due to side effects
- 4. Pregnancy (women found to be pregnant will be referred to prenatal care)
- 5. Miss more than 2 consecutive visits (unless excused by the PI)

Study Enrollment Procedures

Recruitment

We do not anticipate difficulty with the completion of this trial as our study team has demonstrated the ability to recruit a similar population in several previous trials (PCOS studies completed by UPenn and PSU: OWL-PCOS/PPCOS1 /PPCOS2). At both sites we have expert investigators in PCOS to improve external validity and to help overcome any possible recruitment barriers. Subjects recruited at UPenn are drawn from a four state area including Pennsylvania, New Jersey, Delaware, and Maryland. [name] directs the Penn PCOS center which is located at 2 sites (Philadelphia city and in a suburban location - Radnor) and she sees approximately 1000 visits/year exclusively for PCOS. UPenn also has a high patient volume in Reproductive Endocrinology with 22,000 patient visits per year. Hershey Medical Center is the only academic medical center between Philadelphia and Pittsburgh with a large referral area. They have recruited subjects from areas as far away as Scranton/Wilkes Barre (90 miles) to the northeast, and Altoona (150 miles) to the West, Harrisburg (12 miles), York (30 miles), Lancaster (20 miles), State College (90 miles), Williamsport (90 miles), and Allentown (85 miles). The location of the two sites, University of Pennsylvania (UPenn) in an urban setting, and Hershey Medical Center (PSU) in a rural/suburban setting will allow us to recruit from a representative sample of the population.

Clinical Practices of Investigators

Women presenting to the clinical practices of [name], [name], and [name] for consultation for PCOS (after clinical confirmation of their potential eligibility for admission into the study based on inclusion and exclusion criteria) will be approached to participate by the research coordinator or non-care providing physician. In the recruitment visit, study details including the intervention will be explained. Risks and benefits will be thoroughly discussed and consents given to the patient prior to any study procedures being performed. The drugs being utilized in this study are commonly used in current practice and may be familiar to the women interested in participating in the study.

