7.2.8 Week 20 patient contact

This contact will be made to ensure subject compliance with medications, keeping study logs and to review any side effects. Instruction to subject that the ASA 24 (online diet diary recall assessment) to be completed prior to the 24-week visit

7.2.9 Week 24 Final Follow- Up Visit or Early Termination Visit (≥ to 12 weeks of being on study medication)

- 1. Collect menstrual log and review medical history
- 2. Perform Urine pregnancy test
- 3. Record vital signs and biometrics
- 4. Review Hirsutism (F-G) Score/ Acne Assessment
- 5. Fasting blood draw and safety labs
- 6. Complete an oral Glucose Tolerance Test
- 7. PCOSQ, CESD-R, STAI
- 8. Review Hirsutism (F-G) Score/ Acne Assessment
- 9. Complete DXA scan
- 10. Obtain a Transvaginal Ultrasound (TVU)
- 11. Review Adverse Events
- 12. Collect Logs and medication
- 13. Must obtain and record menstrual history
 - Determine need for medroxyprogesterone acetate (if subject has had no menses during the course of this study)

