8.2.1 Protection against Risk of Study Interventions

Study subjects will be carefully screened for medical problems prior to randomization. The risks of the medications used in this study will be lowered through education and frequent follow-up. Study subjects will be monitored monthly in person or by telephone for adverse reactions. Only a limited supply of medication will be dispensed at each visit to encourage compliance with the protocol and prevent a prolonged exposure of an early gestation to medication.

Oral Contraceptive Pill-We will exclude subjects with all absolute contraindications to OCP including a history of thrombophlebitis, known or suspected clotting disorders, cerebrovascular or coronary artery disease or myocardial infarction, known or suspected uterine, cervical or breast neoplasia, history of a benign or malignant liver tumor that developed during the use of OCPs or other estrogen-containing products. Additionally, we will exclude other relative contraindications as listed in the exclusion criteria. Smoking will not be an absolute contraindication. Subjects will be counseled about the risks of OCP, and warning signs for serious adverse events including leg swelling, redness, pain, shortness of breath, racing heart, chest pain, severe and unremitting headache, unilateral weakness or speech disturbance. Subjects will have a scheduled visit or receive communication from the study team monthly and symptoms elicited and recorded as part of the visit.

Worrisome signs will be reported to study physicians immediately for evaluation and management. We will have a low threshold of suspicion for discontinuing medication. We should note that we had no serious adverse events among 49 obese women randomized to a low dose OCP in the OWL-PCOS study (see table 2 for side effects above). Although the OWL-PCOS study showed a significant increase in prevalence of MetS in the OCP arm, only a small proportion of subjects developed DM or hypertension (4.6% and 6.7% respectively after 16 weeks). A fasting glucose level will be evaluated at the 16 week visit and a value >200mg/dl will prevent a subject from continuing in the study. BP will be measured at each visit and a subject with BP>150/100mmHg x2 will be unable to continue in the study.

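### Women terminated for blood pressure before 12 weeks on drug have no full MetS outcome, and the primary logistic regression has no method for missing outcomes

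*Combined protocol and SAP*

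**What the plan says.** - **Termination.** The Study Termination Criteria include "Development of hypertension as defined in the manual of procedures" and "Development of diabetes as defined in the manual of procedures". Section 8.2.1 adds that blood pressure is measured at each visit and "a subject with BP>150/100mmHg x2 will be unable to continue in the study". For the fasting glucose taken at week 16, "a value >200mg/dl will prevent a subject from continuing in the study".
- **Outcome.** MetS is at least three of five criteria. Besides triglycerides and HDL-C these are "BP≥130/≥85mmHg, WC>88cm and fasting glucose≥100mg/dl" (Primary Aim).
- **Early-termination visit.** Table 6 heads the column "Early Termination Visit (> or equal to 12 weeks of medication", and the week-24 visit description (7.2.9) has "Early Termination Visit (≥ to 12 weeks of being on study medication". This visit includes fasting and safety labs, vital signs and biometrics.
- **Blood.** Laboratory Evaluations schedules draws at screening, randomization, week 16 and week 24, with early termination in parentheses and no 12-week condition. Weeks 4 and 8 have vital signs and biometrics only, and may be remote.
- **Analysis.** Statistical Analysis includes all randomized women by arm. It fits a logistic regression to MetS at the end of the trial, with arm and the three stratification factors. Distributions are to be inspected so that missing data can be addressed. If attrition looks like a problem, completers are compared with non-completers. The remark that incomplete data are not dropped belongs to the mixed models for secondary continuous outcomes.
- **Follow-up.** General Design Issues says that all subjects will be tracked to completion, but names no visit or measurement.

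**The concern.** A visit rule, followed exactly, creates missing primary outcomes, and the reason for stopping is related to that outcome. The stop lies above the MetS blood-pressure cut-off, so a woman who meets it already has one of the three criteria she needs. She then leaves without the measurements that would settle the other criteria. A single-time-point logistic regression drops her, although the plan says she is included.

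If such stops differ by arm, the primary contrast is distorted, and the data collected cannot show in which direction. The plan also does not say whether an early-termination value at 12 weeks or later stands in for week 24. That choice would be left until the data are in hand.

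**Working it through.** **1. Who has no outcome.** Blood pressure is checked in person at weeks 4, 8 and 16; week 12 is a patient contact. A blood-pressure stop before 12 weeks therefore comes, in practice, at week 4 or 8. At that point blood pressure and waist may have been measured, but triglycerides, HDL-C and glucose have not been measured since randomization. The early-termination visit is closed to her.

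**2. The plan's own power.** Inputs from Sample Size and Power Calculations: MetS rates 0.26 (metformin), 0.40 (both), 0.50 (OCP); 240 randomized; 15% drop-out; two-sided 0.05. Evaluable: 240 × 0.85 = 204, or 68 per arm. I used a Cochran-Armitage trend test with equally spaced scores (the plan does not state them) and a continuity correction:

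- D = 68 × (0.50 − 0.26) = 16.32; mean rate 0.3867
- s0 = √(0.3867 × 0.6133 × 2 × 68) = 5.679
- s1 = √(68 × (0.26 × 0.74 + 0.50 × 0.50)) = 5.485
- power = Φ((16.32 − 0.5 − 1.96 × 5.679)/5.485) = Φ(0.855) = 80.4%

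The five rows of Table 10 come out at 84.0, 89.2, 80.4, 86.4 and 79.6%, against the stated 84, 89, 80, 86 and 80. The planned OCP versus metformin odds ratio is (0.50/0.50)/(0.26/0.74) = 2.85.

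**3. Effect of the loss.** Let t be the share of an arm lost and f the share of those who are MetS-positive. The observed rate is (p − t·f)/(1 − t). Both t and f are assumptions: t runs from 1.25% (1 of 80) to 5% (4 of 80), and f from 0.75 to 1. The 68 per arm is held fixed, because this loss is counted inside the 15%.

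| Loss | t | f | OCP rate | Metformin rate | OR | Power |
|---|---|---|---|---|---|---|
| None | 0 | – | 0.500 | 0.260 | 2.85 | 80.4% |
| OCP arm only | 1.25% | 0.75 | 0.497 | 0.260 | 2.81 | 79.3% |
| OCP arm only | 1.25% | 1 | 0.494 | 0.260 | 2.78 | 78.2% |
| OCP arm only | 5% | 0.75 | 0.487 | 0.260 | 2.70 | 75.7% |
| OCP arm only | 5% | 1 | 0.474 | 0.260 | 2.56 | 70.5% |
| Every arm | 1.25% | 0.75 | 0.497 | 0.254 | 2.90 | 81.6% |
| Every arm | 5% | 1 | 0.474 | 0.221 | 3.17 | 85.8% |
| OCP arm only | any | 0.50 | 0.500 | 0.260 | 2.85 | 80.4% |

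**4. Why the direction is open.** Loss multiplies an arm's odds by r = (1 − t·f/p)/(1 − t(1 − f)/(1 − p)). For OCP with t = 5%, f = 1: r = 1 − 0.05/0.50 = 0.90, and 2.846 × 0.90 = 2.56. For metformin with the same loss: r = 1 − 0.05/0.26 = 0.808, and 2.846 × 0.90/0.808 = 3.17. With f = 1 the two cancel when metformin loses 0.26/0.50 = 52% of what OCP loses. So four women lost from 80 on OCP are offset by about two from 80 on metformin.

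**5. Baseline adjustment.** If retention depends on arm and final MetS status only, the same factor applies to the adjusted odds ratio. If loss depends only on arm and baseline MetS, the adjusted odds ratio is unbiased.

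**6. Against sampling error.** SE of the log odds ratio = √(1/(68 × 0.26 × 0.74) + 1/(68 × 0.50 × 0.50)) = 0.368, so a 2.85 estimate has a 95% interval of about 1.38-5.85. The largest shifts in the table, to 2.56 or 3.17, are each about 0.29 SE.

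**The case against.** The strongest reply is that this is a small matter with no measured size. That stands as regards size. The stop meets one MetS criterion, not three, so f is unknown. The prior-trial rates in 8.2.1, "4.6% and 6.7% respectively after 16 weeks" for diabetes and hypertension, carry no denominator: 2/49 is 4.1% and 3/49 is 6.1%, so 4.6% cannot come from the 49 women on OCP. The OCP side-effect table for those 49 women has no hypertension row, only one raised reading without hypertension (2.0%). A reader might take 6.7% as the expected loss; the documents do not support that, and they do not say how much fell before week 12.

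Three other stronger readings also fail:

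- **Diabetes stops cause the same early loss.** No glucose is scheduled between randomization and week 16, and the glucose stop is placed at week 16, after the 12-week threshold.
- **The week-16 safety labs are optional.** The word in 7.2.7 most likely covers the research draw. Table 6 lists safety labs at week 16 without the as-needed mark, and 8.2.1 says glucose will be evaluated then.
- **The plan hides harm from OCP.** The hypothesis that OCP raises blood pressure makes loss on OCP plausible, but step 4 shows the bias can go either way.

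It is also fair to say that 12 weeks may be a deliberate minimum exposure, that 204 is a sample-size allowance and not an analysis set, and that the manual of procedures is not available here. None of this gives the primary model a method. Inspecting distributions and comparing completers with non-completers describe missing data; they supply no outcome for these women.

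**Conclusion.** The point holds as a gap between the stated analysis set and what the visit schedule and model can deliver. Women stopped for blood pressure at week 4 or 8 have no full MetS outcome. The primary regression can then be run only on observed cases, with some loss tied to a component of the outcome. Women who leave early for other reasons meet the same missing method, but without this direct link to the outcome.

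The bias is probably small: within the assumed 1.25-5% loss, the odds ratio moves from 2.85 to somewhere between 2.56 and 3.17, and power to between 70% and 86%. The direction is unknown and can turn on one or two women. These figures rest on assumed loss shares, an assumed MetS-positive share, and the planned rates. It should be fixed because the remedy is cheap and settles the rule before results are known.

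**What to change.** Leave the stopping rules unchanged.

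1. Reconcile Laboratory Evaluations, Table 6, 7.2.9 and General Design Issues so that the existing MetS measures (fasting lipids and glucose, blood pressure, waist) are taken whenever participation ends. Take them again at week 24 where the woman consents and is not pregnant.
2. State in Statistical Analysis that the primary outcome is the week-24 value, and whether an early-termination value at 12 weeks or later counts in its place. Fill remaining gaps by multiple imputation of the five components from arm, the three strata, baseline and all post-randomization values, including week-4 and week-8 blood pressure and waist where measured. A value taken before 12 weeks enters as a predictor, not as the 6-month outcome.
3. Report two sensitivity analyses: complete case, and all diabetes or hypertension terminations counted as MetS-positive.

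Cost: item 1 is a small amendment using tests and a visit that already exist, plus a few extra blood draws. At V10.1 (November 2021) of a 2017-2022 trial, it helps only women not yet terminated. Items 2 and 3 are analysis wording and some imputation work on data already collected, and remain useful after the last visit.
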